3.1 General Design

This is a single-group (n=20) open-label pilot study of 6 doses of IV ketamine, 3 doses per week over a 2-week period, followed by a 4-week post-treatment observational period. Symptom levels will be assessed prior to infusion, directly after infusion, 1 and 2 hours after infusion. We will also assess symptoms weekly for 6 weeks after the last ketamine infusion. A study goal is to identify neurobiological biomarkers of treatment response using neuroimaging and blood studies.

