To determine the efficacy of repeated-dose subanesthetic IV ketamine among adolescent patients with treatment resistant depression (TRD). *Hypothesis:* Based on previous results in adults with TRD, we predict that response rates will improve over the course of six treatments of ketamine.

Secondary Objectives:

To explore the durability of antidepressant response to repeated dose of IV ketamine in a 6-week observational period. *Hypothesis:* Based on the inherent neuroplasticity in adolescence due to ongoing neurodevelopment, adolescents may show a more durable clinical response than has been seen in adults.

To study the neurobiological mechanisms of response to ketamine. We will explore how clinical improvement relates to change in brain function, brain connectivity, brain chemistry, and in peripheral blood biomarkers of neuroplasticity and cellular resilience.

3 Study Design

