4.4 Early Withdrawal of Subjects

When and How to Withdraw Subjects

A subject may be withdrawn from the study prior to expected completion for the following reasons:

- Participant experiences adverse side effects to the ketamine treatments that are intolerable to the adolescent or the parent.
- Participant fails to adhere to protocol requirements
- Participant or participant's parent(s) withdraw consent

If a subject exits the study for any reason (withdrawal, non-response, or relapse), he or she will continue his or her pre-study regimens and consult with his or her psychiatrist about the next step in treatment.

Data Collection and Follow-up for Withdrawn Subjects

For all participants, we will request permission during the consent process to collect naturalistic follow-up data through in person visit to clinic or video conference 6 months after the 6-week study period.

The naturalistic follow-up encounter will be as follows:

We will ask permission to contact the family to inquire about the participant. Subjects will be determined lost to follow-up if they do not respond to 4 e-mails to the primary e-mail address of parent(s) or 4 phone calls to their primary number or to their next-of-kin, or to a certified letter.

During the follow up in person visit to clinic or video conference subject will be asked to provide:

- a) A narrative interval history including following elements
 - a. Changes in medications and their effects
 - b. Therapies or other treatments they have undergone and their effects
 - c. Evolution of their symptoms during the interval
 - d. Any hospitalizations including cause and outcome
 - e. Any suicide attempts including precipitating factor (if any) and outcome
- b) Participate in a clinical interview in order for clinician to complete an assessment using CDRS-R, CADSS, CGI, and MADRS.
- c) Complete the BDI-II, Profile of Mood States – Adolescent, SHAPS and TEPS

5 Study Drug

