5.5 Subject Compliance Monitoring

Since the study medication is administered in an infusion unit, compliance with study medication will be measured by whether participants present to infusion visits and cooperate with all procedures of IV ketamine administration. To be compliant with other aspects of the study, participants will be required to attend two MRI scans, six ketamine treatment visits and six weekly follow-up visits. The follow up visits may take place in person or, for subjects who do not reside within convenient travel distance to Minneapolis, via phone or video conference. Study staff will monitor whether the participant is attending these visits. If a participant is not compliant with study procedures, his/her participation in the study will be terminated.

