6.7 Visits 11-16 – Follow-up period

All participants will be asked to speak with the research team for weekly follow-up visits for 6 weeks. Participants will continue to take medications as prescribed by their doctor. At each of these visits, participants will be asked about any medication changes and will complete the same assessments as administered in visit 10 (MADRS, CADSS, POMS-A, SHAPS, TEPS, BDI-II, CGI, CDRS and BPRS).

All participants will be asked to participate in the 6 weekly follow-up visits, regardless of response.

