6.8 Schedule of Events Table

| | Consent | Interview | Questionnaires in-person | MRI | Blood draw | Ketamine infusion |
|---|---------|-----------|--------------------------|-----|------------|-------------------|
| Initial visit | X | X | X | | | |
| Within a week from first visit | | | | X | X | |
| Week 1 *Monday | | | | | | X |
| Week 1 Wednesday | | | | | | X |
| Week 1 Friday | | | | | | X |
| Week 2 Monday | | | | | | X |
| Week 2 Wednesday | | | | | | X |
| Week 2 Friday | | | | | | X |
| Within a week from last infusion | | X | X | X | X | |
| Follow-Up Week 1 | | | X | | | |
| Follow-Up Week 2 | | | X | | | |
| Follow-Up Week 3 | | | X | | | |
| Follow-Up Week 4 | | | X | | | |
| Follow-Up Week 5 | | | X | | | |
| Follow-Up Week 6 | | | X | | | |

*The Monday, Wednesday, Friday schedule does not have to start on a Monday, it can start on a Wednesday or Friday, but treatments will always occur on these days and the total time will always be 2 weeks.

CONFIDENTIAL

This material is the property of the University of Minnesota. Do not disclose or use except as authorized in writing by the study sponsor

7 Statistical Plan

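### Section 3.1 states 4 weeks of follow-up where the visit schedule gives 6; separately, the planned average relapse time has no horizon and no value for participants who do not relapse

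*Combined protocol and SAP*

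**What the plan says.** Section 3.1 describes six infusions over two weeks, "followed by a 4-week post-treatment observational period". Two sentences later the same paragraph says: "We will also assess symptoms weekly for 6 weeks after the last ketamine infusion".

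The rest of the protocol points to six weeks of weekly follow-up:

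- Section 2, secondary objective: "To explore the durability of antidepressant response to repeated dose of IV ketamine in a 6-week observational period".
- Section 5.5, compliance: "six ketamine treatment visits and six weekly follow-up visits".
- Section 6.7, Visits 11-16: "All participants will be asked to speak with the research team for weekly follow-up visits for 6 weeks", and again "All participants will be asked to participate in the 6 weekly follow-up visits, regardless of response".
- Section 6.8, last row of the schedule table: "Follow-Up Week 6".
- Section 11.3 pays for up to six weekly follow-up visits.

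Section 4.4 places the naturalistic contact "6 months after the 6-week study period" without saying which six weeks are meant.

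On relapse, Section 3.3 (item 6) sets a CDRS threshold of at least half the pre-ketamine baseline and dates onset midway between the relapse visit and the preceding response. Section 7.3 plans a time to relapse for each participant, and the Study Summary adds a group average. None of these places states an observation horizon, or what value a participant takes who has not relapsed when follow-up ends. Section 1.4 gives the adult experience as 50% of patients not relapsed at 4 weeks.

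**The concern.** The two statements in 3.1 cover the same period after the last infusion and cannot both be right. Durability is a named secondary objective, with the hypothesis that adolescents may hold their response longer than adults, so the length of observation should be stated once and consistently.

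The larger issue is what is done with the follow-up data. An average relapse time has no defined value for anyone who stays well. If it is taken over observed relapses only, it leaves out the participants with the most durable response. If non-relapsers are given the end-of-follow-up time, it becomes a quantity bounded by the window. Either way it tends to lengthen as the window lengthens, which is the direction the hypothesis predicts. Nor is a mean time comparable with the adult benchmark, which is a proportion at a fixed time.

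**Working it through.** **Step 1. Which follow-up length does the protocol operate on?** Section 11.3 gives a maximum payment that depends on the number of weekly visits, V. The components are 40 dollars for baseline, 20 for the post-treatment clinical assessment, 2 × 40 for the MRI visits, 20 for the 6-month contact and 10 per weekly visit:

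- Total = 40 + 20 + 80 + 20 + 10V = 160 + 10V.
- V = 6: 160 + 60 = 220, the stated figure.
- V = 4: 160 + 40 = 200, which does not match.

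Visits 11 to 16 also number six, and Section 3.2 names Visits 11-16 as a source of the Exit CDRS. No visit, table row or payment stops at week 4.

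**Step 2. Section 4.4.** Two weeks of treatment plus four of follow-up is 6 weeks; two plus six is 8. The phrase in 4.4 therefore fits a 2 + 4 reading. It equally fits loose use of the 6-week observational period named in Section 2. The text does not settle which.

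**Step 3. How far does an average relapse time depend on the window?** The documents give no adolescent relapse data, so this is an illustration. It assumes a constant relapse hazard λ and a relapse-free share S(4) at 4 weeks. The central value of 50% is borrowed from Section 1.4; 30% and 70% are assumed to show the range.

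- λ = −ln S(4) / 4. For 50%: ln 2 / 4 = 0.173 per week.
- Share relapsed by week T: F(T) = 1 − exp(−λT).
- Mean relapse-free time within the window: R(T) = F(T) / λ.
- Mean time among those seen to relapse: [R(T) − T(1 − F(T))] / F(T).

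For 50%: F(4) = 0.500 and F(6) = 0.646; R(4) = 2.89 and R(6) = 3.73 weeks. The mean among relapsers is (2.89 − 4 × 0.500) / 0.500 = 1.77 weeks at T = 4, and (3.73 − 6 × 0.354) / 0.646 = 2.49 weeks at T = 6.

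| Assumed relapse-free at 4 weeks | Relapsed by week 4 | Relapsed by week 6 | R(4), R(6) (weeks) | Mean among relapsers, 4-week window | Mean among relapsers, 6-week window |
|---|---|---|---|---|---|
| 30% | 70.0% | 83.6% | 2.33, 2.78 | 1.61 | 2.14 |
| 50% | 50.0% | 64.6% | 2.89, 3.73 | 1.77 | 2.49 |
| 70% | 30.0% | 41.4% | 3.36, 4.65 | 1.88 | 2.73 |

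At 50%, moving from a 4-week to a 6-week window raises the mean among relapsers by 2.49 − 1.77 = 0.72 weeks (2.49 / 1.77 = 1.41, or 41%) with no change in the relapse process. Within a 6-week window, moving from 30% to 70% relapse-free at 4 weeks, a large real difference in durability, raises it by only 2.73 − 2.14 = 0.59 weeks. The relapse-free proportion at week 4 is the same whichever window is used.

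**The case against.** The strongest reply is that the 4-week phrase is a leftover: one clause, contradicted two sentences later, with every operational section at six. That stands. A reader might infer that the trial carries two designs, or that relapse will have two values depending on which section is followed. The documents do not support this. All participants are asked to attend all six weekly visits regardless of response, so weeks 5 and 6 are observed, and no relapse definition or analysis refers to a 4-week stop.

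It is also fair to say that the figures in Step 3 are not caused by the stray phrase. Correcting 3.1 would leave the average relapse time just as dependent on the window. They illustrate the missing horizon and the missing rule for non-relapsers, and should be read only in that sense.

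A reader might go on to infer a biased comparison with adults. No formal comparison is planned, and Section 2 says only that adolescents may show a more durable response. Section 1.4 does not state the adult scale or relapse definition and gives its 50% for patients, not responders. If five of the ten completers were relapse-free and all five were among nine responders, the responder figure would be 5/9 = 56%. It would therefore be unsound to turn the illustration into expected numbers of relapsing responders in this trial.

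What survives is narrower: a durability hypothesis framed against adults is to be summarised by a quantity that cannot be placed beside the one adult durability figure reported from the investigators' own study.

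**Conclusion.** Two findings of modest weight.

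1. **Consistency.** The 4 weeks in Section 3.1 is contradicted by its own paragraph and by Sections 2, 5.5, 6.7, 6.8 and 11.3. Section 4.4 is ambiguous rather than wrong. Correcting both changes no data collected.
2. **Durability summary.** The average relapse time in the Study Summary and Section 7.3 is incompletely defined and depends on the length of observation. Under a constant hazard, the mean among observed relapsers is 33% to 45% longer over 6 weeks than over 4 (2.14 / 1.61 = 1.33; 2.73 / 1.88 = 1.45) across assumed 4-week relapse-free shares of 30% to 70%. The direction holds throughout that range. The sizes rest on the assumed hazard and on borrowed or assumed shares, and they ignore the midpoint rule in 3.3.

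Neither finding bears on the choice of 20 participants, for which Section 7.1 gives no numerical inputs.

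**What to change.** - **Section 3.1:** reconcile the observational period to 6 weeks, in line with the visit structure.
- **Section 4.4:** state the date from which the 6 months is counted. The paragraph sits under follow-up of withdrawn subjects, so the anchor must also work for early withdrawals. The scheduled end of follow-up does; attendance at Visit 16 does not.
- **Section 7.3:** add the relapse-free proportion among responders at 4 weeks and at 6 weeks after the last infusion. Say at which visit a participant is classed as a responder for this purpose, because the Exit CDRS in 3.2 may itself come from a follow-up visit. If the average relapse time is kept, state its horizon and how participants without relapse enter it.
- **Caveat to include:** the 4-week proportion shares a time point with the adult figure in 1.4, but the adult scale, relapse definition and denominator are not given, so the comparison is descriptive.

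The cost is wording in three sections and one extra descriptive estimate, reported at two time points, from data already being collected. No visits or assessments are added.

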3.2 Primary Study Endpoints

The primary outcome measure is response status as defined by Children's Depression Rating Scale (CDRS) (Poznanski, 1985) Responders will be defined as having a significant reduction in their CDRS score ($\geq 50\%$) whereas non-responders will be defined as subjects whose scores do not show such a significant reduction or whose score increase. The percent change will be calculated by the formula below (Tao, 2009):

$$(\text{Baseline CDRS} - \text{Exit CDRS}) / (\text{Baseline CDRS} - 17)$$

Baseline CDRS: CDRS score obtained on Visit 1 – Baseline Assessment (Section 6.1)
Exit CDRS: the latest CDRS score obtained on Visit 10 - Clinical Assessment (Section 6.6) or Visit 11-16 – Follow-up Period (Section 6.7)

CONFIDENTIAL

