3.3 Secondary Study Endpoints

1. Montgomery-Åsberg Depression Rating Scale (MADRS) (Montgomery & Asberg, 1979) score of $\geq 50\%$. The MADRS has been used in most previous ketamine studies in adults and is designed to be sensitive to change. Although it has not been validated in adolescents, it has been used in several previous treatment studies of adolescent depression (Berard et al., 2006; von Knorring et al., 2006).
2. The Clinician-Administered Dissociative States Scale (CADSS) (Bremner et al., 1998)
3. The Profile of Mood States-Adolescent Version (POMS-A) (Terry et al., 1999)
4. The Beck Depression Inventory-II (Beck, 1988) which has been validated for adolescents (Osman et al., 2004)
5. The four-item positive symptom subscale of the Brief Psychiatric Rating Scale (BPRS) (Overall, 1962) consisting of suspiciousness, hallucinations, unusual thought content, and conceptual disorganization.
6. Relapse will be defined as a CDRS score $\geq 50\%$ of the pre-ketamine baseline. The onset of relapse will be calculated as the day halfway between the date of relapse and the previous date of response.
7. Biological endpoints will include MRI-based measures and blood-based measures of neuroplasticity.
8. The Clinical Global Impressions Scale (CGI) (Guy, 1976)

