6.6 Visit 10 – Clinical assessment and blood draw

Also within one week of the last ketamine infusion, participants will come to the Ambulatory Research Center or participate in a phone or video conference for clinical evaluation to assess their clinical response to the ketamine infusions. At this visit, the following assessments will be completed to determine response to treatment: Columbia Suicide Severity Rating Scale – Since Last Visit (CSSRS-SLV), Montgomery-Asberg Depression Rating Scale (MADRS), Clinician-Administered Dissociative States Scale (CADSS), Profile of Mood States-Adolescent Version (POMS-A), Snaith-Hamilton Pleasure Scale (SHAPS), Temporal Experience of Pleasure Scale (TEPS), Beck Depression Inventory-II (BDI-II), Clinical Global Impression (CGI), and Brief Psychiatric Rating Scale (BPRS). Also, the clinician will complete a Children’s Depression Rating

CONFIDENTIAL

Scale-Revised, a clinical interview with both adolescent and parent/guardian (separately), to assess depression severity. The participant will also be asked to perform the DPX-task.

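### The primary response status uses the latest CDRS from Visits 10 to 16, so it mixes time points, conflicts with section 6.6 and folds durability into the primary outcome

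*Combined protocol and SAP*

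**What the plan says.** Section 3.2 declares response status on the CDRS as the primary outcome. A responder has a reduction of at least 50%, computed as (Baseline − Exit)/(Baseline − 17). The score entering as Exit is "Exit CDRS: the latest CDRS score obtained on Visit 10 - Clinical Assessment (Section 6.6) or Visit 11-16".

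The other relevant statements are these:

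- **Section 6.6** places Visit 10 within one week of the last infusion and says that there "the following assessments will be completed to determine response to treatment". A CDRS-R interview is part of that visit.
- **Section 6.7** lists the CDRS at each of Visits 11 to 16 and states: "All participants will be asked to participate in the 6 weekly follow-up visits, regardless of response".
- **Section 2** has a separate secondary objective: "To explore the durability of antidepressant response to repeated dose of IV ketamine in a 6-week observational period". **Section 3.3** lists relapse as a secondary endpoint ("Relapse will be defined as a CDRS score" at or above a stated fraction of baseline).
- **Section 3.1** gives two follow-up lengths. Treatment is "followed by a 4-week post-treatment observational period", yet also: "We will also assess symptoms weekly for 6 weeks after the last ketamine infusion".
- **Section 5.5** counts the six weekly visits among the requirements and adds: "If a participant is not compliant with study procedures, his/her participation in the study will be terminated".
- **Section 7.2** admits to the primary analysis every participant who completes six infusions, with no condition on follow-up attendance.
- **Section 7.3** gives as primary analysis a paired t test of each participant's lowest post-treatment score against baseline. It plans no estimate or test of response status.

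**The concern.** A primary outcome should say when it is measured. Here the time is set by the last visit a participant happens to attend. Two groups with identical symptom courses but different attendance could report different responder rates.

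Even with perfect attendance there is a mismatch. The outcome would then be status at about week 6, while section 6.6 ties the determination of response to Visit 10. A participant who responded and relapsed during follow-up would count as a primary non-responder and also as a relapse under section 3.3, so a secondary question would enter the primary one.

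At stake is how the responder rate can be read. This is a pilot that section 5.2 describes as a step toward a randomized trial, so readers will want to know whether the rate is acute or sustained response.

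**Working it through.** The plan states no figure that could be reproduced for this outcome, so the check is mainly of the text, followed by simple arithmetic on size.

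**1. When can Exit fall?**
- Earliest: Visit 10 only, within 7 days of the last infusion (section 6.6).
- Latest: Visit 16. Counting weeks from the last infusion as in section 3.1, 6 × 7 = day 42. If the 4-week period in section 3.1 governs, 4 × 7 = day 28.
- No section narrows this range to one visit or window.

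**2. What does the rule give?**
- Full attendance: Visit 16 for everyone, about week 6.
- Follow-up ended or final visits missed: the last CDRS obtained, back to Visit 10. Section 5.5 provides for termination, and section 7.2 keeps such a participant in the primary analysis if six infusions were completed.

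**3. When does the visit change the classification?**
A responder has (B − Exit)/(B − 17) ≥ 0.5, so Exit ≤ 0.5B + 8.5. At the entry minimum B = 36 the cut is 26.5; at an assumed B = 60 it is 38.5. With B = 60, a participant at or below 38.5 at Visit 10 and above it at Visit 16 is a responder if follow-up stops at Visit 10 and a non-responder if it is completed. The symptom course is the same in both cases.

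**4. How much does each such participant matter?**
One changed status moves the rate by 1/n.

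| n in the analysis | Step per participant |
|---|---|
| 20 (planned) | 1/20 = 5.0 points |
| 18 (assumed completers) | 1/18 = 5.6 points |
| 16 (assumed completers) | 1/16 = 6.25 points |

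**5. How does that compare with sampling error?**
Exact (Clopper-Pearson) 95% intervals at n = 20, around an assumed 10 responders:

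| Responders | Rate | 95% CI |
|---|---|---|
| 8 | 40% | 19.1% to 63.9% |
| 10 | 50% | 27.2% to 72.8% |
| 12 | 60% | 36.1% to 80.9% |

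The half-width at 10/20 is (72.8 − 27.2)/2 = 22.8 points. Two changes in the same direction move the rate by 2/20 = 10 points, which is well inside it.

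**6. Which analyses use Exit CDRS?**
- The section 7.3 symptom t test uses the lowest post-treatment score, so it does not depend on the Exit rule.
- The neuroimaging t tests compare scans before and after treatment and do not use response status.
- The blood assays are to be correlated with a response profile that is not defined. They are affected only if that profile means this status.

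**The case against.** The strongest reply is that the rule is deterministic. It names a set of visits and takes the last, all participants are asked to attend every visit, and section 5.5 allows phone or video contact for those who live far away. On this view the only gap is an unnamed target visit and an unstated rule for missed visits, and naming Visit 16 would be the smaller edit. The first part stands: it is wrong to say the outcome has no rule, and with full attendance everyone is classified at the same visit. But the protocol never names Visit 16 as the target. Naming it would settle the timing, but it would leave the conflict with section 6.6 and the overlap with the secondary durability objective.

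Three stronger readings are tempting, and the documents do not support them:

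- **The schedule restricts Exit to Visit 10.** A reader might infer this because the table in section 6.8 ticks Interview only at the initial visit and within a week of the last infusion. The table is too coarse for that. It ticks no questionnaires on infusion days, although section 6.3 requires several, and section 6.7 expressly lists the CDRS at Visits 11 to 16.
- **The rate would shift by tens of points.** A reader might project this from the adult series in section 1.4 (90% cumulative response, 50% not relapsed at 4 weeks). That needs an assumed relapse pattern taken from about ten adults, and it treats relapse as permanent loss of response. The protocol gives no expected number of early leavers.
- **The bias has a known direction.** Section 4.4 mentions leaving for non-response or relapse, but section 6.7 keeps everyone in follow-up regardless of response. The direction cannot be settled from the text.

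Medication changes during follow-up could also affect a late score. Section 6.7 asks about them, but sections 5.2 and 5.6 have current antidepressant treatment continue throughout, which limits that worry without removing it.

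**Conclusion.** The point holds as an endpoint-definition problem that should be fixed. Followed exactly, section 3.2 yields status at about week 6 for full attenders and status at some time from within one week to about six weeks for the others. That conflicts with the role section 6.6 gives Visit 10, and it brings durability into the primary outcome. Section 7.3 then leaves the declared outcome without an analysis.

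The numerical effect is modest as far as it can be known: 5 points per affected participant at n = 20, with any total resting on an assumed number of early leavers. One or two changes fall within sampling error. The case therefore rests on what the rate means rather than on a demonstrated bias, and the planned t tests on symptoms and imaging are not called into question by it.

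**What to change.** **Section 3.2.** Define Exit CDRS as the CDRS-R at Visit 10, within one week of the last infusion. State a rule for a missed Visit 10, for example counting the participant as a non-responder, with a sensitivity analysis that uses the first follow-up CDRS instead.

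**Section 3.3.** Add response at the final weekly follow-up visit as a named secondary endpoint, and use Visits 11 to 16 for relapse and durability.

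**Section 7.3 and the Study Summary.** Make the Visit 10 responder proportion, with an exact 95% interval, the analysis of the primary outcome. State its denominator under section 7.2 and keep the t test as supporting.

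**Section 3.1.** Reconcile the 4-week and 6-week follow-up lengths, so that the final follow-up visit is unambiguous.

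No new visit or measurement is needed, because the Visit 10 CDRS-R is already collected. The cost is a few sentences and a protocol amendment, which section 10 requires to go to the IRB. The scientific price is that the primary outcome would no longer reflect sustained response, which would be reported as secondary.
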